Sub-study 1 has the following aims:

- 1a) Investigate the effectiveness of the multidisciplinary intervention alone and as a supplement to TKA in comparison with TKA alone, on pain measured by the Knee Injury and OA Outcome Score (KOOS) at 1-year follow-up (primary outcome)
- 1b) Investigate the effectiveness of the multidisciplinary intervention alone and as a supplement to TKA on the KOOS subscores function and stiffness
- 1c) Evaluate adverse events in the three study arms during the first year following randomization

Sub-study 2 has the following aims:

- 2a) Evaluate the adherence and feasibility of the multidisciplinary intervention in a feasibility study
- 2b) Determine the effects of the multidisciplinary intervention, on lower extremity strength and range of motion at 12 months follow-up
- 2c) Investigate the effects of the multidisciplinary intervention on health-related quality of life at 12 months follow-up

Sub-study 3 has the following aims:

- 3a) Investigate the cost-effectiveness of the multidisciplinary intervention alone and as a supplement to TKA, in comparison with TKA alone
- 3b) Assess the use of health care resources at 2-year follow-up in the 3 treatment arms
- 3c) Assess the use of medication at 2-year follow-up in the 3 treatment arms

Sub-study 4 has the following aims:

- 4a) Compare the effect in the 3 treatment arms on sports and recreation, walking and physical performance 2 years following the intervention
- 4b) Investigate the longitudinal relationship between pain catastrophizing, fear of movement and depression, on functional levels in the 3 treatment arms during the 2 years following the intervention
- 4c) Identify barriers to and benefits of increased adherence to physical activity in patients with painful knee OA

Methods/Design

This is a multicenter randomized controlled trial with three arms: 1) PT + CBT intervention alone, 2) PT + CBT in combination with TKA, and 3) standard care control group receiving TKA. The protocol adheres to the CONSORT guidelines and to the principles of the Declaration of Helsinki, and is approved by the The Regional Medical Research Ethics committee of Health East of Norway (2017/968).

Project arrangements, method selection and analyses

Intervention

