All patients scheduled for TKA at the two surgical clinics (i.e., Lovisenberg Diaconal Hospital (Lovisenberg), Kysthospitalet Hagevik (Hagevik)) will be screened prior to their consultation with their orthopedic surgeon. The screening will be performed using a validated prioritization algorithm developed by Escobar and Riddle⁽⁷⁻⁹⁾, using the following preoperative predictors: preoperative pain and function; presence of widespread pain; and the following additional factors: anxiety/depression; pain catastrophizing; coping strategies. The additional predictors were selected based on findings from our previous studies^(10, 11) and the literature⁽¹²⁾. Based on this screening, each patient will be categorized as either inappropriate/inconclusive, or appropriate for surgery. The surgeon and patient will be blinded to the result of the screening during the consultation. The surgeon will receive a sealed envelope with the result of the screening. After the surgeon and the patient have jointly decided to schedule the patient for TKA, the surgeon will open the envelope. Patients categorized as inconclusive/inappropriate will be invited to participate in the study. Patients who consent to participate will then be randomly allocated to one of the intervention groups or the control group using allocation numbers in sealed envelopes. The envelopes will be prepared before initiation of the trial by an independent staff member, and distributed to the two study sites (Lovisenberg and Hagevik). The envelopes will be kept in a locked location only available to the research assistants at each study site. Reasons for not participating will be recorded.

Figure 2 – allocation of patients into 3 treatment arms

Patients who meet the following inclusion criteria will be eligible for the study: 1) scheduled for TKA for OA at Lovisenberg or Kysthospitalet Hagevik, Bergen, 2) Charnley comorbidity classification A, B or C, 3) ASA grade 1 and 2, and 4) BMI<40, 5) able to read and write in Norwegian. In addition, the patient must be identified as being at high risk for an unsuccessful outcome after TKA based on cutoff scores on 2 or more of the following screening criteria, whereof one must be within the physical components, and one must be within the psychological components of the screening criteria:

- Age <55 years
- Preoperative pain and function level: The Knee Injury and OA Outcome Score (KOOS) pain and physical scale combined⁽⁹⁾, cutoff ≤ 22 .

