Table 1 study measures

Construct assessed	Data collection instrument	Time of collection
Primary outcome measure	Proms	
Pain	Pain subscale of the KOOS	0, 3, 6, 12 and 24 months
Secondary outcome measures	Data collection instrument	Time of collection
	Proms	
Pain, symptoms, ADL, QOL, sport & recreation	The five individual subscales of the KOOS	0, 3, 6, 12 and 24 months
Self-reported level of physical activity	HUNT2, Stages of Change physical activity	0, 3, 6, 12 and 24 months
Co-morbidity	The Self-Administered Co-Morbidity Questionnaire	0 months
Pain, interference with functioning, number of painful sites	Brief pain inventory	0, 3, 6, 12 and 24 months
Sleep	Pittsburgh Sleep Quality Index	0, 3, 6, 12 and 24 months
Catastrophic thinking related to pain	Pain Catastrophizing scale	0, 3, 6, 12 and 24 months
Locus of control	The Health Locus of Control Scale	0, 3, 6, 12 and 24 months
Pain-related fear of movement	The Fear-Avoidance Belief Questionnaire	0, 3, 6, 12 and 24 months
Mood states	The Hospital Anxiety and Depression Scale	0, 3, 6, 12 and 24 months
Health-related quality of life	EuroQol-5 (EQ5D-5L)	0, 3, 6, 12 and 24 months
Natural feeling of joint	Forgotten Joint Score	0, 3, 6, 12 and 24 months
Anchor measures of satisfaction	Patient acceptable symptom state	0, 3, 6, 12 and 24 months
	Treatment failure	0, 3, 6, 12 and 24 months
	Global perceived effect	0, 3, 6, 12 and 24 months
	Objective measures	
Functional lower extremity test	The 30 second sit to stand test	0, 3, 6, 12 and 24 months
Walking	6 minutes walk test	0, 3, 6, 12 and 24 months
Body mass index	Weight from baseline to follow-up	0, 3, 6, 12 and 24 months
Time in active position/number of steps	The ActivePal Professional Single Axis accelerometer	0, 3, 6, 12 and 24 months
Radiological measurements	Weightbearing AP, lateral view, Rosenberg view and long leg weightbearing AP view (HKA)	0 and 24 months
Other measurements		
Adverse events	Physiotherapy-reported, patient-reported, medical records	0, 3, 6, 12 and 24 months
	Registry-based data	
Use of health care resources	The KUHR-system	0, 3, 6, 12 and 24 months
	The Norwegian Patient Registry	0, 3, 6, 12 and 24 months

	FD trygd social security data base	0, 3, 6, 12 and 24 months
Outcomes, Feasibility study		
Adherence to intervention	Records, physiotherapists. Data, eTherapy.	0, 3, 6, 12 and 24 months
Acceptability of the intervention	Questionnaires, interviews	0, 3, 6, 12 and 24 months

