Adverse events	Patients, physiotherapists, medical records	0, 3, 6, 12 and 24 months
Recruitment, screening, randomization	Flow chart, inclusion and exclusion	0, 3, 6, 12 and 24 months
Retention in study/loss to follow-up	Loss to follow-up, crossover	0, 3, 6, 12 and 24 months

Registry-based data

Use of health care resources: registry data from the KUHR-system (i.e., control and payment of reimbursements to health service providers), the Norwegian Patient Registry (NPR) and FD Trygd social security database. All information will be anonymized and linked to each patient using a unique ID number generated prior the start of this study. Data on revision surgery and deep prosthetic infections will be retrieved from the Norwegian Arthroplasty Registry⁽²⁶⁾.

Other measures

Adherence with AktivA: The physiotherapists will monitor patients' adherence with the AktivA program during the 12 weeks. Adherence will be measured as the total number of the 24 sessions completed. Good compliance will be defined as participation in 75% or more of the exercise sessions, medium compliance will be defined as participation in 50-74% of the sessions, and poor compliance will be defined as participation in less than 50% of the sessions.

Compliance with the e-therapy program: Good adherence to the e-therapy program will be defined as completing 75% of the content; medium compliance will be defined as completing 50-74% of the program, and poor compliance will be defined as completing less than 50% of the sessions. In addition, time used in the program will be assessed.

Power calculation and sample size

The primary outcome measure is KOOS pain subscale, 12-month follow-up. The minimal perceptible clinical improvement (MPCI) for KOOS has been determined to be 10 points⁽¹³⁾ which will be considered a minimal clinically important change. The power will be set to 80%, the level of significance at 1%, and the standard deviation of the measurements considered equal in both groups at 16, resulting in a sample size of 62 patients in each treatment group. The attrition rate will be set to 20% to account for drop-out and crossovers. Therefore, we will include and randomize a total of 230 patients.

Statistical analysis

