Data analyses will be performed using SPSS version 24.0 (IBM, Armonk, NY) and STATA version 14.2. Differences between the intervention and control group will be analyzed using responder analysis based on the OMERACT-OARSI responder criteria^(27, 28). Differences between the intervention and control groups at 12 months will also be analyzed using ANOVA. Non-normally distributed data will be analysed using the Kruskal-Wallis test. Differences over time at 3, 6 and 12 months will be analysed using mixed models for repeated measures to account for dependencies caused by each patient being measured several times. P-values <0.05 will be considered statistically significant, and all estimates will be reported with 95% confidence intervals. Effect sizes will be calculated for group differences using Cohen's coefficient *d*. A *d*-value ≥ 0.40 will be considered a clinically meaningful difference⁽²⁹⁾. All analyses will be performed based on the intention to treat principle.

Economic evaluation

The cost-effectiveness analysis will be based on the Norwegian healthcare system. A societal perspective will be used as recommended by Russel et al⁶⁷. A Markov decision model will form the theoretical framework for a cost-effectiveness analysis to estimate the costs and benefits for patients in the two intervention groups and the control group. With this model, simulation will be performed of long-term health benefits, health care costs and cost-effectiveness of the specified interventions. The main variables will be QALYs based on the EQ5D, combined with use of health care resources and use of medication. The incremental cost-effectiveness ratio (ICER) will be used to summarize the cost-effectiveness of each of the intervention groups, compared to the control group. Sensitivity analyses will be performed to test the stability of the conclusions. According to the literature, a clinically relevant difference in EQ5D between the groups would be 0.08⁶⁸. Keeping alpha to 5% and power to 80%, we would need 42 individuals in each group.

Given we plan to enroll 62 in each group, our study is sufficiently powered to reveal a clinical relevant difference also for this secondary aim.

Timelines

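### Intention-to-treat is prescribed for every analysis; by-arm adverse event counts should stay, but a table by treatment received is needed beside them

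*Protocol*

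**What the plan says.** The last sentence of the protocol's Statistical analysis section reads "All analyses will be performed based on the intention to treat principle". It carries no qualification. The methods named before it (responder analysis, ANOVA, Kruskal-Wallis, mixed models, Cohen's d) are methods for outcome scores, and no method for adverse events is described.

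Aim 1c of Sub-study 1 is to "Evaluate adverse events in the three study arms during the first year following randomization". Under Methods/Design the arms are "1) PT + CBT intervention alone, 2) PT + CBT in combination with TKA, and 3) standard care control group receiving TKA", so one arm is non-surgical and two are surgical.

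Under Recruitment and allocation, the decision to operate precedes the invitation to the trial: "After the surgeon and the patient have jointly decided to schedule the patient for TKA, the surgeon will open the envelope". Every participant has therefore already agreed to TKA when randomized.

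The section on power and sample size expects some participants to change treatment: "The attrition rate will be set to 20% to account for drop-out and crossovers". It gives no separate rate for crossovers. Table 1 names crossover once, as "Loss to follow-up, crossover", in the block of feasibility-study outcomes.

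For the main trial, Table 1 takes adverse events from these sources: "Physiotherapy-reported, patient-reported, medical records". It also schedules Norwegian Patient Registry data at 0, 3, 6, 12 and 24 months. The section on registry-based data adds: "Data on revision surgery and deep prosthetic infections will be retrieved from the Norwegian Arthroplasty Registry".

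**The concern.** The trial tests PT+CBT as a substitute for TKA, so the harm of surgery compared with no surgery matters when hypothesis 1 is interpreted. Crossover from the non-surgical arm to TKA is plausible: participants were already scheduled for the operation, they are not blinded, and the plan allows for crossovers.

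Read literally, the rule counts adverse events by randomized arm only. A patient assigned to PT+CBT alone who is later operated on and has a deep prosthetic infection is then an event of the exercise and CBT arm, although a patient without a prosthesis cannot have that event. A patient assigned to TKA who is never operated on counts in the surgical denominator without having been exposed to surgery. Both move the arms towards each other. A reader who takes the by-arm figures as the risk of the treatments received would see too little excess risk from surgery.

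**Working it through.** The protocol states no figure for adverse events, so there is nothing of its own to reproduce. The check has two parts: what the wording implies, and how large the dilution can be.

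**Wording.** The rule covers all analyses, and aim 1c is an analysis by arm with the clock starting at randomization. Together they give by-arm counts. No sentence provides for a second grouping or says how an event after a crossover TKA is attributed.

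**Size.** Let

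- pT = risk of an adverse event within 12 months with TKA, and pN = the risk without it (assumed; not in the protocol);
- c = proportion of the non-surgical arm that has TKA (assumed; the protocol gives only a 20% allowance shared with drop-out);
- s = proportion of a surgical arm that does not have TKA (assumed).

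If risk depends only on receipt of TKA:

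- non-surgical arm: R1 = c·pT + (1 - c)·pN
- surgical arm: R3 = (1 - s)·pT + s·pN
- by-arm difference: R3 - R1 = (pT - pN)·(1 - c - s)

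The proportional reduction is c + s, whatever pT and pN are. With assumed risks across a range:

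| pT / pN | c | s | R1 | R3 | By-arm difference (points) | Difference for surgery received (points) | Reduction |
|---|---|---|---|---|---|---|---|
| 5% / 1% | 5% | 0 | 1.20% | 5.0% | 3.80 | 4.0 | 5% |
| 5% / 1% | 20% | 0 | 1.8% | 5.0% | 3.2 | 4.0 | 20% |
| 5% / 1% | 20% | 10% | 1.8% | 4.6% | 2.8 | 4.0 | 30% |
| 10% / 2% | 5% | 0 | 2.4% | 10.0% | 7.6 | 8.0 | 5% |
| 10% / 2% | 20% | 0 | 3.6% | 10.0% | 6.4 | 8.0 | 20% |
| 10% / 2% | 20% | 10% | 3.6% | 9.2% | 5.6 | 8.0 | 30% |
| 20% / 5% | 5% | 0 | 5.75% | 20.0% | 14.25 | 15.0 | 5% |
| 20% / 5% | 20% | 0 | 8.0% | 20.0% | 12.0 | 15.0 | 20% |
| 20% / 5% | 20% | 10% | 8.0% | 18.5% | 10.5 | 15.0 | 30% |

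On the ratio scale, at 10% / 2% with s = 0, the risk ratio falls from 10/2 = 5.0 to 10/3.6 = 2.8 at c = 20%.

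**In patients.** With 230 randomized, an arm holds about 230/3 = 77. At c = 20% that is 0.20 × 77 = 15.4 crossovers. The extra events counted in the non-surgical arm are 15.4 × (pT - pN): 0.6, 1.2 and 2.3 patients for the three pairs of risks. For the middle pair, the standard error of the by-arm difference is √(0.10 × 0.90/77 + 0.036 × 0.964/77) = 0.040, or 4.0 points. The shift of 8.0 - 6.4 = 1.6 points is 0.4 of a standard error.

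**The case against.** The strongest reply has five parts.

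**By-arm counting is right for aim 1c.** The aim asks about events in the study arms from randomization. Later surgery and its complications are a real consequence of being assigned to PT+CBT first, and only this comparison is randomized. This stands. A reader might infer that intention-to-treat is the wrong principle for harms here; the protocol does not support that, and the by-arm table must remain.

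**The application to adverse events is inferred.** The rule closes a paragraph on outcome scores, and no adverse event analysis is described. This stands as a caution: the protocol nowhere says explicitly that adverse events are analyzed by intention-to-treat. The inference comes from the word all, read with an aim framed by arm.

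**Safety sets belong in the SAP.** The SAP was not among the documents reviewed, and the absence of a safety population from the protocol is not a fault. But the point concerns a rule that the protocol does state. A SAP that added an analysis by treatment received would depart from its literal wording, so the sentence is the place for the change.

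**The data exist.** A reader might infer from the position of crossover in Table 1 that the main trial cannot place events before or after surgery, or cannot report risk by treatment received. That does not follow. Medical records and Norwegian Patient Registry data are scheduled main-trial sources and could supply TKA dates. What can be said is that no main-trial item is designated for the purpose.

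**The size is hypothetical.** This stands. A c of 20% would use up the whole allowance that the plan shares between drop-out and crossover. The resulting shift is small against sampling error, and no conclusion of the trial is shown to change.

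**Conclusion.** The point holds as an improvement to a stated rule. Followed literally, the protocol yields adverse event counts by randomized arm only. These compare the assigned strategies validly, but they attribute the TKA complications of crossovers to PT+CBT and shrink the contrast for surgery received by the factor (1 - c - s). With s = 0 the reduction is 5% at c = 5% and 20% at c = 20%.

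The result rests on the assumption that event risk depends only on receiving TKA. That ignores differences between patients who cross over and those who do not, and it ignores timing: crossovers operated on late in the year leave less time for complications inside the 12-month window, which lessens the dilution. The direction is towards understating the excess risk of surgery received. The amount in this trial cannot be computed, so none of the figures above should be read as an estimate for it. The primary outcome is not affected.

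**What to change.** In the Statistical analysis section, limit the intention-to-treat sentence to the efficacy analyses and the by-arm adverse event table. Add a supplementary adverse event table by treatment received, classing each event as before or after any TKA. This classification is also informative for the surgical arms, where follow-up from randomization includes time on the waiting list.

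Take the TKA dates from the medical records and Norwegian Patient Registry data already scheduled in Table 1. List crossover among the main-trial measures in Table 1 as well as among the feasibility outcomes.

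The cost is one reworded sentence, one added table and one table entry, with no new data source. The downside is that the treatment-received table is not protected by randomization. It should be labelled descriptive and presented beside the by-arm table, not in its place.

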A multidisciplinary intervention in total knee arthroplasty - a multicenter, randomized controlled trial in osteoarthritis patients (MULTI-KNEE trial).

This is a protocol for a multicenter, three-armed, randomized controlled trial (RCT). An estimated one in five patients undergoing total knee arthroplasty (TKA) does not improve in pain and function, suggesting that among the 6466 patients who underwent primary TKA in Norway in 2016, more than 1200 patients derived little or no benefit from the surgery and continue to experience chronic pain. In addition, these numbers suggest that more than 100 000 000 NOK are spent every year on an invasive treatment with questionable effect⁽¹⁾. This study will evaluate the effect of a multidisciplinary intervention delivered either as a substitute, or in addition to, TKA for patients identified as being at risk for non-improvement after TKA.

Hypotheses, aims and objectives

The overall aim of this study is to test the effectiveness of a 12-week integrated Physiotherapy (PT) group exercise program in combination with cognitive behavioral therapy (CBT) support, delivered by physiotherapists, in patients with knee osteoarthritis (OA) who are on a waiting list for TKA and who are identified as being at risk for non-improvement based on a set of preoperative criteria. The effects of the integrated PT exercise program and CBT will be evaluated both as a substitute for TKA and as a supplement to TKA in comparison to TKA alone. We hypothesize that for patients identified as being at risk for postoperative non-improvement: 1) the effect of PT exercise and CBT alone will be equivalent to surgical treatment alone, and 2) the effect of PT exercise and CBT in combination with surgical treatment will be better than surgical treatment alone. The effects of the three treatments will be evaluated in terms of pain relief (primary outcome), functioning and quality of life (QOL) (secondary outcomes) at 12-month follow-up. The study includes a pilot study with 15 participants prior to the full-scale study.

This large study consists of four sub-studies and a pilot study, each with individual aims.

The pilot study has the following aims:

- To evaluate the feasibility of the multidisciplinary intervention alone and as a supplement to TKA
- To evaluate the rate of recruitment, patients' willingness to participate and adherence to the intervention
- Investigate patients' experiences with participation in the study

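### With three competing strategies, ICERs against TKA alone cannot show which intervention is preferable, and one ratio becomes unstable if QALYs turn out equal

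*Protocol*

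**What the plan says.** The Methods/Design section describes three arms: "1) PT + CBT intervention alone, 2) PT + CBT in combination with TKA, and 3) standard care control group receiving TKA". Aim 3a, under sub-study 3, is to "Investigate the cost-effectiveness of the multidisciplinary intervention alone and as a supplement to TKA, in comparison with TKA alone".

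The Economic evaluation section plans a Markov model covering all three groups, in which "simulation will be performed of long-term health benefits, health care costs and cost-effectiveness of the specified interventions". On inputs it says "The main variables will be QALYs based on the EQ5D, combined with use of health care resources and use of medication". The result is to be summarised as follows: "The incremental cost-effectiveness ratio (ICER) will be used to summarize the cost-effectiveness of each of the intervention groups, compared to the control group". On uncertainty it says only "Sensitivity analyses will be performed to test the stability of the conclusions".

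The section names no contrast between the two intervention arms, no ranking of strategies, no net benefit and no threshold. Its only sample-size figure is 42 per group for an EQ-5D difference of 0.08, and it describes this aim as secondary.

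Hypothesis 1 is that "the effect of PT exercise and CBT alone will be equivalent to surgical treatment alone". The three treatments are to be evaluated "in terms of pain relief (primary outcome), functioning and quality of life (QOL) (secondary outcomes) at 12-month follow-up".

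**The concern.** A patient can receive only one of the three strategies, so a decision maker has to choose among three. Two ratios against a common comparator answer a narrower question, namely whether each intervention is acceptable relative to TKA alone. If both are, the choice between them rests on the extra cost and extra QALYs of adding TKA to PT+CBT, and the plan does not compute that.

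The two ratios may also point in opposite directions. If PT+CBT alone saves money and loses some QALYs, a large ratio is favourable. If the combination costs more and gains QALYs, a small ratio is favourable. Set side by side they do not form a scale.

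A further difficulty affects only the ratio of PT+CBT alone to TKA. The trial hopes to find these two equivalent. If that holds for QALYs as well as for pain, the ratio divides a substantial cost difference by something close to zero.

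At stake is whether the economic result can inform a choice among three strategies, and whether the substitution question yields an interpretable number.

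**Working it through.** **The plan's own figure.** The 42 per group cannot be reproduced, because no EQ-5D SD is stated. Solving backwards (two-sided 5%, 80% power, normal approximation) gives SD = 0.08 × √(42/2) / (1.960 + 0.842) = 0.131. This figure does not decide the point; it only supplies one SD for step 4.

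**Inputs.** The protocol gives no costs, QALYs or threshold. All such values below are assumptions for illustration. The 62 per arm is the protocol's figure.

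**1. What the planned summary would report.** Units are thousand NOK and QALYs. ICER = ΔC/ΔQ, and incremental net benefit (INB) = λΔQ − ΔC, both against TKA alone, with threshold λ = 500.

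| Strategy | Cost | QALYs | ΔC | ΔQ | ICER vs TKA | INB vs TKA |
|---|---|---|---|---|---|---|
| PT+CBT alone | 50 | 1.40 | −100 | −0.02 | 5000 saved per QALY forgone | −10 + 100 = +90 |
| TKA alone | 150 | 1.42 | – | – | – | 0 |
| PT+CBT plus TKA | 180 | 1.50 | +30 | +0.08 | 375 per QALY gained | 40 − 30 = +10 |

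**2. The contrast that is not planned.** PT+CBT plus TKA against PT+CBT alone: (180 − 50)/(1.50 − 1.40) = 130/0.10 = 1300 per QALY. Since 1300 is below 5000, TKA alone is extendedly dominated.

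PT+CBT alone passes against TKA at any threshold below 5000, and the combination at any threshold above 375. Both therefore pass from 375 to 5000. Within that range PT+CBT alone has the highest net benefit up to 1300, and the combination above 1300. The switch point is absent from the planned summary.

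**3. The same two ratios can go with opposite rankings.** Keep the combination at +30/+0.08. Change PT+CBT alone to ΔC = −10, ΔQ = −0.002.

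- ICERs against TKA: 10/0.002 = 5000, and 375. Both are unchanged.
- INB at λ = 500: PT+CBT alone −1 + 10 = +9; combination +10. The combination now ranks first.

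Identical reported ICERs thus accompany +90 against +10 in one case and +9 against +10 in the other. The ambiguity comes from the form of the summary and does not depend on one choice of values.

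**4. Stability of the PT+CBT versus TKA ratio if QALYs are equal.** An EQ-5D difference is used here as a stand-in for a QALY difference. SE = SD × √(2/62).

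- SD 0.131: SE = 0.0235, 95% half-width 1.96 × 0.0235 = 0.046.
- SD 0.25: SE = 0.045.

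In a simulation with an assumed saving of 90,000 NOK (SE 15%) and a threshold of 500,000 NOK per QALY:

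| True difference | SD | Central 95% of ICER (million NOK per QALY) | Central 95% of INB (NOK) |
|---|---|---|---|
| 0 | 0.131 | −62 to +62 | 55,000 to 125,000 |
| 0 | 0.25 | −32 to +32 | 39,000 to 141,000 |
| −0.08 | 0.131 | 0.6 to 2.7 | 15,000 to 85,000 |

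With a true difference of 0 the denominator is positive in 50% of replicates, so the sign of the ratio carries no information. INB stays stable around 90,000. With a true difference of −0.08 and the smaller SD, the ratio is usable.

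**The case against.** The case on the other side has real force.

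- **No wrong strategy is selected.** A reader might infer that the plan would recommend the combination when PT+CBT alone is the efficient choice. The text does not support that. It promises a ratio for both interventions and states no rule that picks one. In the illustration both would be reported as acceptable. What stands is that the choice between them is left undetermined.
- **Dominance is not hidden altogether.** A reader might infer that comparisons with TKA cannot reveal that TKA is itself dominated. Simple dominance would show at once, as lower cost with more QALYs. Where TKA lies between the other two in cost, as here, the two ratios in order of cost fall from 5000 to 375, and a falling sequence signals extended dominance. What is missing is the ratio left after TKA is removed, 1300.
- **Equivalence in pain is not equality in QALYs.** A reader might infer that the denominator vanishes whenever hypothesis 1 is true. The hypothesis is judged at 12 months with pain as the primary outcome and no stated margin; the denominator is EQ-5D QALYs with long-term benefit simulated. The instability arises only if equivalence extends to QALYs over the model horizon. It does not touch the combination's ratio. The standard errors above are within-trial sampling errors, not those of the long-term model.
- **The framing matches the aims.** Aim 3a and both hypotheses compare with surgery alone, and a separate analysis plan, not at hand, may add detail on thresholds and uncertainty. This is a reason to keep the TKA comparisons. It does not make them a sufficient summary, and here the protocol does more than stay silent: it names the statistic and the comparator.

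**Conclusion.** The point holds as a matter of analysis choice. The stated summary answers whether each intervention is acceptable against TKA alone, but cannot by itself say which of the two is preferable. In the illustration the ambiguity spans thresholds from 375 to 5000 thousand NOK per QALY: PT+CBT alone is best from 375 to 1300 and the combination above that, with both passing against TKA throughout. The width of that range depends wholly on assumed costs and QALYs. The ambiguity itself does not, as the pair of examples with identical ratios shows.

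The instability of the substitution ratio is conditional on QALYs being close to equal over the model horizon. Under that condition, and with the assumed saving and SDs, the ICER is uninformative while incremental net benefit remains interpretable.

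The aim is secondary, and allocation, data collection and the primary result are unaffected. The change is still worth making because the three-arm model already yields what is needed.

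**What to change.** Replace the ICER sentence in the Economic evaluation section with a fully incremental analysis of the three strategies:

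1. Rank the three by cost, remove dominated and extendedly dominated strategies, and report sequential ICERs. Report the contrast of PT+CBT plus TKA with PT+CBT alone as part of this.
2. Report incremental net monetary benefit over a stated range of thresholds, with its uncertainty (for example as acceptability curves across all three strategies).
3. Keep the two comparisons with TKA alone, which answer aim 3a, and label any saving per QALY forgone as such so that it is not read as a cost per QALY gained.

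No new data are needed. The cost is revised wording and a little extra analysis on costs and QALYs that the Markov model already estimates for all three groups.
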